### **Primary Outcomes - Medications**

Total number of Medications: Data sources include the participant's VUMC 'pre-hospital medication list', patient/family interview, pharmacy refill records, Controlled Substance Monitoring Database (CSMD), and outside hospital/PAC medical records. We include both prescription and over-the-counter medications (OTC) (vitamins, herbal supplements also included) administered by the following routes: oral, intravenous, intramuscular and ophthalmologic medications. All participants and/or their surrogates receive a baseline structured interview and chart review to determine any medication that has the potential to be continued at the time of hospital discharge to including pre-hospital medications and active in-hospital medications not on the pre-hospital medication list. Pre-hospital medications are confirmed by patient/ family interview and pharmacy refill records (including mail-order pharmacies) for the three months prior to hospitalization. Patient/surrogate are given specific prompts if they report no OTC usage, for example, asking them if they take anything for sleep disturbances, constipation, or allergies. If a patient is admitted from SNF or an outside hospital, we will request a copy of the MAR for the past 30 days. Current medications are defined as those taken within 30 days prior to hospitalization. At PAC discharge, the discharge medication list serves as the outcome data source. During follow-up calls at 7 and 60 days, study team asks the patient or surrogate for the status of each medication on the enrollment medication list to determine if and how they are taking it. Then the study team prompts for any new medications the patient may be using. In preparation for the 90-day visit, the study team completes a pharmacy record review similar to enrollment. At the 90-day visit, the study PharmD or NP reviews all the medication bottles in the home and asks the patients if and how they are using each.

PIMs are defined by previously published lists including the recently updated Beers criteria, the STOPP criteria, as well as the RASP list, for which there is a large degree of overlap. The total number of PIMs is the sum of medications that are found on any of these explicit lists. The total number of medications related to geriatric syndromes will be based on the detailed lists of specific medications we developed in preparation for this proposal. We also sought to determine the total number of medications that may be contributing to or exacerbating geriatric syndromes in this patient population. To enable this, we developed a unique Shed-Meds knowledge base. Our research team consisted of: PhD Gerontologists, Geriatricians, Hospitalists, Pharmacists, Geriatric Nurse Practitioners, and Specialists (e.g., Urologist, Geriatric Psychiatrist). Based on an extensive literature review, we first compiled a list of all medications potentially contributing to the following six geriatric syndromes: cognitive impairment, delirium, depression, urinary incontinence, unintentional weight loss/appetite decrease and falls. Next, we held a series of team meetings to review each medication list in the context of each syndrome with the goal of reaching consensus based on the following criteria: (1) evidence-based recommendations (randomized controlled trials, meta-analysis, systematic review articles); (2) expert clinical opinion (care practice guidelines, expert consensus, review articles); (3) associated with  $\geq 5\%$  side effect incidence per the Lexicomp Online® database and/or FDA approved package inserts; and, (4) the potential for over-prescribing in this population.

Drug Burden Index (DBI): A DBI score is calculated separately for anticholinergic (DBIAC) and sedative medications (DBIS), which have been strongly linked to functional impairment, falls and delirium. The drug burden is the sum of each individual anticholinergic/sedative medication's prescribed daily dose divided by the sum of the minimum effective dose (as estimated by the FDA minimum recommended dose) and the patient's daily dose. The DBI includes over-the-counter medications. We will calculate the DBI at the time of randomization, hospital discharge, PAC discharge, and all follow-up timepoints. Importantly, the DBI captures reductions in dose, even when total number of medications is not reduced.

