## **STUDY DESIGN**

The study is a 5-year, randomized controlled clinical intervention trial at a singular academic medical center.

Primary Outcomes are change in total number of medications including the number of potentially inappropriate medications, number of medications associated with geriatric syndromes, and medications that contribute to anticholinergic and sedative drug burden.

Secondary Outcome is the impact of deprescribing on prevalence and severity of geriatric syndromes, medication adherence, and functional health status.

Eligible patient population is aged 50 years or older, experiencing polypharmacy as defined by 5 or more home medications, and hospitalized at VUMC with a referral to partner post-acute care facility.

Exclusion criteria include limited life expectancy (less than 6 months), non-English speaking, no telephone, homeless or incarcerated, enrolled in another drug trial, and expected to discharge from VUMC in less than 48 hours.

The primary study setting is Vanderbilt University Medical Center (VUMC), a private, non-profit, tertiary care teaching organization located in Nashville, Tennessee. The medical center is a principal referral center for physicians and patients throughout the Southeast, and it serves a diverse population in terms of income, geography, and education level. We will work with patients discharged to 20 SNFs and 2 IPRs within a nine-county radius of Nashville. The target PACs are all for-profit and comparable to PACs in the middle TN area based on publicly reported staffing and quality indicators ([www.medicare.gov](http://www.medicare.gov)).

The timeline for the study is 5 years with enrollment beginning in March 2017 and enrollment closing at the end of October 2020.

The Shed-MEDS intervention is a multistep deprescribing protocol which considers patient and disease factors, life expectancy, goals of care, and appropriate treatment targets. Medication-specific factors such as drug-drug interactions, drug-disease interactions, and drug-specific safety profiles are also incorporated. Finally, patient preferences and primary prescriber input are key to final deprescribing actions by identifying the medications patients are willing to discontinue and seeking their primary prescriber's agreement. In this intervention, deprescribing is defined as either stopping a medication or reducing the dose/frequency of a medication.

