## **PARTICIPANT RECRUITMENT AND ENROLLMENT**

### **Eligibility Screening and Recruitment**

Vanderbilt Institutional Review Board (IRB) permits a record review to screen patients for research studies, similar to a limited HIPAA waiver. Screening is conducted every weekday by the project coordinator, data

manager, or research assistant. The screening process begins with a structured query of the medical record system (EMR). The physical therapy department (PT) developed a report specifically for the Shed-MEDS team that queries every patient in Vanderbilt University Hospital (regardless of ‘inpatient’ or ‘observation’ status) aged 50 and over who has been evaluated by PT and recommended for SNF placement. All new patients on this report are added to a screening panel in the EMR and subsequently reviewed for the following inclusion and exclusion criteria:

Inclusion Criteria: (1) we confirm that all patients are over the age of 50. The original criteria included patients 65 years and older, but the age limit was lowered to age 50 after four months of initial study enrollment due to a large proportion of hospitalized patients aged 50-64 meeting all eligibility criteria. (2) Next the “Prior to Admission List” in the EMR is reviewed to confirm the patient has five or more medications administered via oral, sublingual, nasal, inhaled, ophthalmic, transdermal, subcutaneous, rectal, intramuscular, intravenous, and peg tube routes. (3) The patient’s county of home residence appears on the screening panel, and they must reside in one of nine surrounding counties.

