### Pre-Review (Target Medications for Deprescribing)

[figure not shown]
Following the baseline patient/surrogate interview, a study clinical reviewer (pharmacist, geriatric nurse practitioner, or physician) receives the reconciled total enrollment medication list. Using medical record data only such as the history and physical, lab values, physician notes, etc., reviewers will first identify a Medication – Indication pairing for each medication (i.e., clinical reviewers try to establish an indication diagnosis or symptom which the medication treats). If an indication does not exist, “no indication indicated” is specified. For each medication recommended for deprescribing, the reviewer chooses one of the following actions: (1) Stop prior to hospital discharge without need for monitoring; (2) Stop prior to hospital discharge with symptoms/physiologic monitoring; (3) Stop at specified time point following hospital discharge; (4) Reduce over time with monitoring until medication is stopped; (5) Reduce to lower dose without need for monitoring; (6) Reduce to lower dose with symptoms /physiologic monitoring. Then the clinician selects a de-prescribing rationale, and they may select more than one rationale (i.e., choose all applicable rationales) from Table 2.

All medications, both prescription and OTC including vitamins and herbal supplements, are reviewed for potential deprescribing. Select medication classes will not be under consideration for active deprescribing, which include the following:

- Anti-rejection medications for organ/ bone-marrow transplantation
- Chemotherapeutic medications for the treatment of known solid organ or hematologic malignancy.

The above medications may be deprescribed during the study period; however, it would solely be under the direction and recommendation of the primary treatment team or primary prescriber of the medication.

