## STATISTICAL CONSIDERATIONS

### Sample Size and Randomization

Figure 1 illustrates the flow of participants through the study and estimated total sample sizes during each study phase based on prior data. The overall effectiveness of the intervention will be evaluated based on the primary outcome measure, which is total medication count. Based on current enrollment rate, we estimate that approximately 144 patients per year will enroll in the study, or 576 across all four years of enrollment. Among those, we estimate that 27.5% will either die or otherwise be lost from the study prior to the 90-day post PAC discharge follow up period. Thus, across all four years of enrollment, an estimated 420 patients will contribute measurements at 90 days. Although 567 is the expected total enrollment, we conservatively use 420 to estimate the statistical power associated with the assessment of overall effectiveness (i.e., overall completion rate) rather than enrollment rate, to account for estimated attrition across all study phases.

Preliminary data is available for the effect of deprescribing on the reduction in the counts of total medications. Our pilot intervention (N=40) was associated with roughly a 50% reduction in the count of total medications from enrollment to hospital discharge, whereas a roughly 25% reduction was observed in the control group receiving routine hospital care. Using these preliminary data and mixed-effects Poisson regression methods, we implemented a simulation-based power analysis wherein we assumed that this effect would be attenuated by 20% at SNF discharge, and again by 20% at the 90-day follow up. Using a sample size of 420, there is greater than 95% power to detect a 50% versus 25% reduction in total medications. There is approximately 90% power to detect a 30% versus 25% reduction in total medications, and 80% power to detect a 27.5% versus 25% reduction in total medications. Thus, the target sample size provides some protection against effects that are substantially smaller than that observed in our preliminary data.

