## Outcomes

Hypotheses 1a-1b: The effect of the intervention on the total number of medications, PIMs, and medications associated with geriatric syndromes at hospital discharge, SNF discharge, and at 90-days following SNF discharge will be assessed using mixed effects Poisson regression, allowing for overdispersion (more or less variability than is expected under the Poisson regression model), and adjusting for measurement time point (as a categorical covariate) and the total number of medications at participant enrollment. The within-subject correlation among repeated measurements will be modeled using a random intercept term, indexed by subject. The intervention effect at each time point will be summarized using a Wald-type 95% confidence interval. Statistical significance will be indicated if the 95% confidence interval excludes the value zero (i.e., the Poisson regression intervention effect under the null hypothesis). Model fit will be assessed by examining the associated Pearson residuals and using other graphical methods. Alternative regression techniques may be used in the case of poor fit, for example, negative-binomial regression.

Hypothesis 1c: The effect of intervention on the anticholinergic and sedative medication drug burden scores at hospital discharge, SNF discharge, and 90-days following SNF discharge will be assessed using linear mixed effects regression, adjusting for measurement time point, and using a random intercept term indexed by subject. Intervention effects will be summarized using 95% confidence intervals. Model fit will be assessed using residual diagnostics and graphical methods. Due to the constrained nature of the score values (0-1 for anticholinergic and sedative drug burden scores), an alternative method may be required, such a ‘beta’ regression, which is suitable when such scores frequently occur at a boundary (0 or 1).

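### The primary medication count is limited to four routes, while eligibility counts eleven and the deprescribing review has no route limit

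*Combined protocol and SAP*

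**What the plan says.** Under Descriptions of Assessments, Primary Outcomes - Medications, the total number of medications covers prescription and over-the-counter drugs "administered by the following routes: oral, intravenous, intramuscular and ophthalmologic medications". Sample Size and Randomization says that overall effectiveness is judged on "the primary outcome measure, which is total medication count". The model under Outcomes adjusts for "the total number of medications at participant enrollment" and states no route rule for it.

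Eligibility Screening and Recruitment sets the threshold of five medications over drugs "administered via oral, sublingual, nasal, inhaled, ophthalmic, transdermal, subcutaneous, rectal, intramuscular, intravenous, and peg tube routes".

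Pre-Review (Target Medications for Deprescribing) has no route limit: "All medications, both prescription and OTC including vitamins and herbal supplements, are reviewed for potential deprescribing". Its exceptions are by class ("Select medication classes will not be under consideration for active deprescribing", namely anti-rejection and chemotherapeutic drugs). The section on studying a vulnerable population adds that antiepileptics given for a seizure disorder are continued. Neither exception is by route.

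Study Design states that "deprescribing is defined as either stopping a medication or reducing the dose/frequency of a medication". A change of route is neither of these.

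**The concern.** Three parts of the protocol use three different scopes for what counts as a medication, and the narrowest belongs to the primary outcome. The intervention can succeed on an inhaled, nasal, transdermal, subcutaneous or rectal drug without that success entering the count. In the other direction, a drug that passes from a counted to an uncounted route between hospital, post-acute care and home leaves the count although the patient still takes it.

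The companion measures make the text harder to apply. Potentially inappropriate medications, medications associated with geriatric syndromes and the Drug Burden Index carry no route limit, so a drug could be counted as potentially inappropriate without being part of the total. Because the covariate's route rule is unstated, baseline and outcome could also be counted on different bases.

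**Working it through.** The plan gives no figure on routes, so there is nothing to reproduce. The check is a comparison of lists, followed by algebra on what the mismatch can do.

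**Step 1: the lists** (ophthalmic and ophthalmologic taken as the same route)

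| Route | Eligibility | Primary count |
|---|---|---|
| oral, intravenous, intramuscular, ophthalmic | yes | yes |
| nasal, inhaled, transdermal, subcutaneous, rectal | yes | no |
| sublingual, PEG tube | yes | no, unless read as oral |

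Eleven routes less four leaves seven uncounted. If sublingual and PEG tube are read as oral, 7 − 2 = 5 remain.

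**Step 2: inputs for the algebra**

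- Reductions of 50% versus 25% (pilot) and 27.5% versus 25% (smallest effect with stated power), from Sample Size and Randomization.
- Enrollment list B: not stated. The 14 and 15 in the Overview are counts at hospital and SNF discharge in an earlier cohort. The pilot figures suggest more: 12.6 / 0.50 = 25.2 and 6.5 / 0.25 = 26.0, although deprescribed drugs there include dose reductions. I use B = 15 and B = 25 as assumptions.
- Share s of the list on uncounted routes: not stated. Assumed 5% to 30%.
- Switches per patient: not stated. Assumed 0.1 to 1.0.

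**Step 3: deprescribing proportional across routes, no switching**

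With reductions a (intervention) and c (control), the counted means are (1 − s)B(1 − a) and (1 − s)B(1 − c). The factor (1 − s) cancels from the ratio: 0.50 / 0.75 = 0.667 and 0.725 / 0.75 = 0.967, whatever s is. The counted difference is (1 − s)B(a − c):

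| B | s | 50% vs 25% | 27.5% vs 25% |
|---|---|---|---|
| 15 | 0 | 3.75 | 0.375 |
| 15 | 5% | 3.56 | 0.356 |
| 15 | 30% | 2.63 | 0.263 |
| 25 | 0 | 6.25 | 0.625 |
| 25 | 5% | 5.94 | 0.594 |
| 25 | 30% | 4.38 | 0.438 |

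If all variance scaled with the mean, the standard error of the log ratio would grow by 1/√(1 − s): 1.03 at 5% and 1.20 at 30%. The planned model also has a random intercept, whose variance does not grow this way, so these factors are nearer an upper bound.

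**Step 4: switching**

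If the same fraction w of remaining drugs moves to uncounted routes in both arms, (1 − w) also cancels. Now suppose that there is no true difference (25% in both arms, B = 15, mean 15 × 0.75 = 11.25) and that the intervention arm has d extra net switches per patient from counted to uncounted routes:

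| d | Rate ratio (11.25 − d)/11.25 | Apparent reduction 1 − (11.25 − d)/15 |
|---|---|---|
| 0.1 | 0.991 | 25.7% |
| 0.375 | 0.967 | 27.5% |
| 1.0 | 0.911 | 31.7% |

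The excess that would mimic 27.5% versus 25% is 0.025 × B: 0.375 drugs at B = 15 and 0.625 at B = 25. Nothing in the documents says that such an excess would occur.

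**The case against.** A reader might set the uncounted drugs against the smallest detectable effect: 5% to 20% of 14 drugs is 0.7 to 2.8 drugs, against 0.025 × 14 = 0.35. The documents do not support that comparison. Uncounted drugs are not lost effect, 14 is a discharge count from an earlier cohort and not the enrollment base, and the 5% to 20% is an assumption. Under proportional deprescribing, the loss from a difference of 0.35 is only 5% to 20% of 0.35, or 0.02 to 0.07 drugs.

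A reader might also infer that the endpoint misses what the intervention acts on, or that it is biased in favor of the intervention. Neither follows. Oral drugs are counted, and the companion primary measures have no route limit. Switches run both ways, a change from intravenous to oral stays within the counted routes, and none of the six deprescribing actions in the Pre-Review is a change of route. Nor does an outcome count below five do harm in itself, since no rule requires five at follow-up.

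The best defense is that the four-route list is merely incomplete wording. The same paragraph describes a baseline review of any drug that might be continued and a 90-day check of every bottle in the home. At 7 and 60 days, staff ask whether and how each enrollment drug is taken, so a change of route could be recognized. This stands as evidence that the data exist. It does not settle the count: those sentences describe collection, nothing calls the route list illustrative, and no rule says how a drug that has changed route is scored.

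**Conclusion.** The inconsistency is real and lies in the current text. Taken literally, the primary count omits seven routes that count for eligibility and are open to deprescribing, or five on the more generous reading of oral. Stops on those routes go unregistered, and switches across the boundary are scored as stops or additions.

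The size cannot be computed from the documents. With deprescribing proportional across routes and switching equal between arms, the rate ratio is unaffected; precision and the absolute difference suffer. Bias between arms requires switching, or the pattern of deprescribing by route, to differ by arm. The figures for B, s and d illustrate the mechanism and do not estimate what happened in this trial. The passages should be reconciled because the rule governs the primary outcome and correcting it is cheap.

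**What to change.** In Primary Outcomes - Medications:

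- Define the total count on one route list at least as wide as the eleven routes used for eligibility. Those eleven still fall short of all medications (topical and otic are absent), so say whether other routes count.
- Apply that list identically to the enrollment covariate in the model, hospital discharge, PAC discharge and every follow-up.
- State that the same drug continued by another route counts as continued, neither stopped nor new.
- Leave the potentially inappropriate medication, geriatric-syndrome medication and Drug Burden Index measures without a narrower route limit.
- Keep any four-route count as a sensitivity analysis.

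The cost is protocol wording and a derivation rule. Interviews, pharmacy records, facility lists and the bottle review already supply full medication lists. If the wider list was used in practice, only the text needs correcting; if four routes were used, the report should say so.
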